### 1.1.1 OVERVIEW OF STUDY TERMS

**Distal Pancreatectomy.** Distal pancreatectomy (removal of the distal pancreas +/- spleen) is indicated in nonmetastatic PDAC, and other neoplasms when disease is localized in the pancreatic tail, as well as in certain patients with chronic pancreatitis. A variant technique of distal pancreatectomy, termed radical antegrade modular pancreateosplenectomy (RAMPS) is often used specifically for malignancies of the pancreas. Pancreatic surgery is technically difficult and highly morbid, with POPF being the most feared complication by clinicians and patients.

**Postoperative Pancreatic Fistula (POPF).** POPF results when digestive enzymes normally secreted by the pancreas leak into the abdominal cavity following an operation, leading to a wide range of inflammatory and auto-digestive complications. POPF is defined by the International Study Group of Pancreatic Fistula (ISGPF) as an amylase level obtained from drainage fluid or abscess of greater than three times the upper limit of normal, starting from the third postoperative day (POD3). POPF is further classified by the ISGPF into biochemical leaks (asymptomatic elevations in amylase from surgical drain fluid that do not require additional treatment), Grade B POPF (requiring percutaneous or endoscopic drainage), or Grade C POPF (resulting in organ failure); together, Grades B/C constitute clinically-relevant POPF (crPOPF). Rates of POPF following distal pancreatectomy range from 20-50% with an average of 30%, with a 10-year average of at OHSU of 30.9% for all POPF and 11.3% for crPOPF.

[figure not shown]
**Sphincter of Oddi.** The Sphincter of Oddi is a smooth muscle valve located at the Ampulla of Vater that regulates the flow of bile and pancreatic secretions into the duodenum. Following distal pancreatectomy, the resting muscle tone of the Sphincter of Oddi may act as a dam, causing the “path of least resistance” for pancreatic secretions to be the cut edge of the pancreas, resulting in POPF as secretions exit into the abdominal cavity and cause an intense autodigestive and inflammatory reaction.

### 1.1.2 OVERVIEW STUDY INTERVENTION(S)

**Botulinum Toxin (BTX).** BTX is a neurotoxin produced by the bacterium *Clostridium botulinum*, which secretes eight exotoxins, (A, B, C(1), C(2), D, E, F, G), all of which block the release of acetylcholine (the primary neurotransmitter at the neuromuscular junction) by cleaving soluble N-ethylmaleimide sensitive fusion protein (SNAP) Receptors (SNARE), leading to muscle paralysis. A commercial formulation of BTX (onabotulinumtoxinA; Botox) has been used for decades with great efficacy in multiple conditions, including strabismus, dystonias, spastic movement disorders, headaches, hyperhidrosis, as well as innumerable cosmetic applications such as reducing the prominence of wrinkles. BTX has an excellent safety profile, with one systematic review of 36 randomized controlled trials noting no serious adverse events.

**Botulinum Toxin Injection to Sphincter of Oddi:** Endoscopic injection of BTX into the lower esophagus is a well-described and FDA-approved treatment for achalasia, and BTX injection into the Sphincter of Oddi is a well-described treatment for Sphincter of Oddi Dysfunction. Injection of BTX into the sphincter of Oddi (Figure 1) performed a median of 6 days prior to distal pancreatectomy reduced POPF rates, but not when performed at a median of one day pre-operatively. This is suspected to be due to the fact that BTX reaches maximal paralytic efficacy at one week.

**Figure 1: Botulinum Toxin Mechanism and Endoscopic Injection Method**

**Figure: Botulinum toxin (Botox) injection method** (A) Normal stimulation of muscle contraction by acetylcholine. (B) Botulinum toxin inhibits muscle contraction by inhibiting release of acetylcholine. (C) An endoscopic sclerotherapy needle is used to make an injection of botulinum toxin at the major papilla, causing paralysis of the Sphincter of Oddi. Figure images obtained from [https://www.hopkinsmedicine.org/gastroenterology\\_hepatology/\\_pdfs/pancreas\\_biliary\\_tract/sphincter\\_of\\_odd\\_i\\_dysfunction.pdf](https://www.hopkinsmedicine.org/gastroenterology_hepatology/_pdfs/pancreas_biliary_tract/sphincter_of_odd_i_dysfunction.pdf)

## 1.2 STUDY RATIONALE

The overall objective of this application is to establish the preliminary efficacy and safety of Sphincter of Oddi BTX injection in the prevention of POPF in the setting of a phase II clinical trial. The central hypothesis is that BTX injection is both safe and efficacious in the prevention of POPF. The rationale for this study is that prevention of POPF would enhance postoperative recovery and quality of life in patients undergoing distal pancreatic resections. These results are expected to have a significant positive impact on clinical practice by improving the perioperative care of patients undergoing distal pancreatectomy for pancreatic cancer and other nonmalignant conditions.

## 1.3 RISK/BENEFIT ASSESSMENT

### 1.3.1 KNOWN POTENTIAL RISKS

Botulinum toxin (onabotulinumtoxinA; Botox) has been used for decades with great efficacy in multiple conditions. BTX has an excellent safety profile, with one systemic review of 36 randomized controlled trials noting no serious adverse events, with focal weakness at/around the injection site being the only mild-moderate adverse event that occurred more often than controls, which is not a relevant risk for endoscopic injection. Post-marketing reports indicate that the effects of all botulinum toxin products may spread from the area of injection to produce symptoms consistent with botulinum toxin effects. These may include asthenia, generalized muscle weakness, diplopia, ptosis, dysphagia, dysphonia, dysarthria, urinary incontinence and breathing difficulties, depending on the site of injection. These symptoms have been reported hours to weeks after injection. Swallowing and breathing difficulties can be life threatening and there have been reports of death. The risk of symptoms is probably greatest in children treated for spasticity but symptoms can also occur in adults treated for spasticity and other conditions, particularly in those patients who have underlying conditions that would predispose them to these symptoms. In unapproved uses, including spasticity in children, and in approved indications, cases of spread of effect have been reported at doses comparable to those used to treat cervical dystonia and at lower doses.

In cases of endoscopic BTX injection, side-effects apart from asymptomatic serum lipase elevations or mild pancreatitis have not been previously reported when administered for Sphincter of Oddi dysfunction, post-cholecystectomy biliary pain, or for prevention of POPF.

Risks specific to endoscopy represent additional study-related risks, and include postinterventional pancreatitis defined by the Atlanta criteria which includes two of the following: 1) abdominal pain consistent with acute pancreatitis; 2) serum lipase  $> 3$  ULN; 3) characteristic imaging findings). Rare risks with the upper endoscopy procedure include cardiopulmonary compromise with procedural sedation, intraprocedural hemorrhage, and bowel perforation.

### 1.3.2 KNOWN POTENTIAL BENEFITS

Immediate potential benefits include a reduced risk of POPF per other studies, which may result in shorter hospital stay and quicker postoperative recovery on average. Long-term potential benefits include the possibility of a higher chance of receiving life-prolonging adjuvant chemotherapy with the avoidance of POPF (due to the study intervention), which would otherwise have delayed or disqualified a patient from adjuvant chemotherapy.

## 2. OBJECTIVES AND ENDPOINTS

### 2.1 PRIMARY OBJECTIVE AND ENDPOINT

Primary Objective	Endpoint	Start	End
Evaluate the efficacy of pre-operative BTX injection compared to no therapy for the prevention of clinically relevant	Rate of clinically relevant (Grade B and Grade C) POPF following distal pancreatectomy/RAMPS,	Day of Surgery	Postoperative Day 30

POPF	defined by standard biochemical definitions of POPF per the ISGPF criteria		
------	--	--	--

## 2.2 SECONDARY OBJECTIVES AND ENDPOINTS

Secondary Objective	Endpoint	Start	End
Evaluate the safety of pre-operative BTX injection into the Sphincter of Oddi	Rate of serious adverse events following BTX injection defined as: pancreatitis requiring hospitalization, gastrointestinal hemorrhage or perforation, other events delaying time to surgery or receipt of surgery, or grade 3 or higher AEs attributable to BTX	Day of study intervention	30 days following surgery or study intervention or until date of surgery
Evaluate the efficacy of pre-operative BTX injection compared to no therapy for the prevention of all POPF	Rate of any POPF following distal pancreatectomy/RAMPS, defined by standard biochemical definitions of POPF per ISGPF criteria	Day of Surgery	Postoperative day 30

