## **SUMMARY OF CHANGES**

## SYNOPSIS

Full Study Title	A Phase II Study of Pre-operative Endoscopic Botulinum Toxin Injection in the Prevention of Postoperative Pancreatic Fistula following Distal Pancreatectomy
Protocol #	22619
Coordinating Center	OHSU, Knight Cancer Institute
Clinical Phase	Phase II - Single Agent
Study Description	Pancreatic resections are inherently morbid operations with complication rates of approximately 40%, the most feared of which is leakage of pancreatic digestive enzymes into the abdominal cavity, termed postoperative pancreatic fistula (POPF). POPF occurs in approximately 30% of distal pancreatectomies, and can dramatically alter the recovery pathway. Pre-operative endoscopic botulinum toxin (BTX) injection into the Sphincter of Oddi has been hypothesized to reduce the rate of POPF following distal pancreatectomy. The present study is a single-arm Phase II interventional study investigating the use of endoscopic botulinum toxin injection into the Sphincter of Oddi prior to distal pancreatectomy to prevent POPF. Intervention will occur 7-14 days prior to planned distal pancreatectomy, and further data collection/treatment will occur per standard of care. Safety of the intervention will be assessed, and patients will be compared to matched historical patients for analysis of POPF rates.
Primary Objective	To determine the effect of pre-operative endoscopic BTX injection on clinically relevant POPF rates following distal pancreatectomy
Secondary Objectives	1) To determine the safety of pre-operative endoscopic BTX injection 2) To determine the effect of pre-operative endoscopic BTX injection on the rate of all POPF (biochemical and clinically relevant) following distal pancreatectomy
Exploratory Objectives	To evaluate differences in: 1) crPOPF, 2) POPF, 3) postoperative length of hospital stay, 4) rate of Clavien-Dindo grade III or greater complications, 5) rate of percutaneous drainage, 6) rate of unplanned re-operation, using a historical population matched for potential confounding clinicopathologic variables.
Primary Endpoint	Rate of clinically relevant POPF (crPOPF) in intervention group
Secondary Endpoints	1) Rate of serious adverse events following endoscopic BTX injection (e.g., clinical pancreatitis, bleeding, perforation, or other events delaying time to surgery or receipt of surgery) 2) Rate of any POPF in intervention group

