### 7.4.4 MANAGEMENT OF SERIOUS COMPLICATIONS FROM STUDY INTERVENTION

**Pancreatitis:** Any patient with abdominal pain, nausea, and intolerance to oral intake will be evaluated for pancreatitis and managed per the standard of care depending on severity of pancreatitis (see American Gastroenterological Association guidelines).

**Gastrointestinal Bleeding:** Patients reporting hematemesis, hematochezia, or melena following study will be evaluated by phone, in clinic, or the emergency department as their clinical status dictates. Most gastrointestinal bleeding following endoscopy is self-limited and otherwise asymptomatic and not considered a serious complication. If clinically significant bleeding occurs, defined as that accompanied by new anemia, hypotension, or other signs/symptoms of significant blood loss, patients will be further evaluated in the emergency department and treated per the standard of care with serial evaluation of hemoglobin/hematocrit, PT/INR, vitals/physical exam, and receive endoscopic, intra-arterial, or surgical management as indicated.

**Gastrointestinal Perforation:** Patients experiencing new severe abdominal pain following discharge from the endoscopic procedural unit will be evaluated in clinic or in the emergency department as dictated by clinical status. Patients with gastrointestinal perforation will be treated as clinically indicated, typically with surgical intervention.

**BTX-Specific Complications:** Patients experiencing BTX-related complications will be managed according to the clinical scenario. Serious allergy-spectrum reactions (e.g., anaphylaxis) will be noted during the observation period and managed accordingly by the clinical staff. Other reactions such as local weakness are predominantly reported in cases of skeletal muscle-adjacent injections. No specific management is required in most cases, however new-onset symptoms following BTX injections will be evaluated by phone or in clinic as indicated, and managed appropriately.

Patients will be counseled on warning signs for the above serious complications prior to and after BTX injection.

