### 8.1.5 ADVERSE EVENT EVALUATION

Toxicities and adverse experiences will be assessed using the [NCI CTCAE 5.0](#). Safety will be monitored by assessing physical examination, vital signs, body height (screening only) and weight as clinically indicated. Additionally, hematology, chemistry, coagulation, urinalysis, thyroid function, and pregnancy will be assessed as clinically indicated.

Adverse events will be monitored from the time the participant receives treatment on study. Participants will be instructed to report all AEs during the study and will be assessed for the occurrence of AEs throughout the study, including and up to 30 days. Due to the known excellent safety profile of botulinum toxin and FDA-approval for endoscopic injection for achalasia, AEs grade 1-2 will not be collected during the study. AEs Grade 3 or higher must be recorded on the source documents and eCRFs regardless of the assumption of a causal relationship with the study drug.

Abnormal laboratory values will only be recorded as an AE if determined to be clinically significant by the investigator.

For details on AE collection and reporting, refer to Section 10.

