#### 10.2.2 SERIOUS ADVERSE EVENT (SAE)

An AE or suspected adverse reaction is considered "serious" if, in the view of either the Investigator or Sponsor-Investigator, it results in any of the following outcomes:

- Death,
- A life-threatening adverse event,
- In-patient hospitalization or prolongation of existing hospitalization,
- A persistent or significant incapacity or substantial disruption of the ability to conduct normal life functions, or
- A congenital anomaly/birth defect.
- Pancreatitis requiring hospitalization
- GI bleeding requiring hospitalization
- GI perforation requiring hospitalization
- Any procedure-related complication resulting in delay of surgery

Important medical events that may not result in death, be life-threatening, or require hospitalization may be considered serious when, based upon appropriate medical judgment, they may jeopardize the participant and/or participant may require medical or surgical intervention to prevent one of the outcomes listed in this definition. Examples of such medical events include:

- Allergic bronchospasm requiring intensive treatment in an emergency room or at home,
- Blood dyscrasias or convulsions that do not result in in-patient hospitalization, or
- The development of drug dependency or drug abuse.

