### 11.4.2 ANALYSIS OF THE SECONDARY ENDPOINT(S)

#### 11.4.2.1 *Rate of serious adverse event*

Using the safety analysis set, the incidence of serious adverse events following endoscopic BTX injection into the sphincter of Oddi as a single agent will be determined for participants undergoing distal pancreas resections. The 95% confidence interval will be reported with the point estimate of SAE rate.

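### The secondary safety endpoint for the injection has an unresolved end date and an event definition that differs between Sections 2.2, 10.2.2 and 10.2.4

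*Combined protocol and SAP*

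**What the plan says.** The endpoint is a rate of serious events after the injection. Five places in the combined protocol and SAP bear on it.

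- **End date.** The End column of Section 2.2 reads "30 days following surgery or study intervention or until date of surgery". Sections 8.5 (follow-up) and 10.5 (event recording) run to 30 days after injection or 30 days after surgery, taking the longer.
- **Endpoint definition.** Section 2.2 lists pancreatitis that leads to admission, GI hemorrhage or perforation without qualification, other events that delay or prevent surgery, and grade 3+ events attributable to BTX. The Synopsis gives an illustrative list: "e.g., clinical pancreatitis, bleeding, perforation, or other events delaying time to surgery or receipt of surgery".
- **General definition of serious.** Section 10.2.2 includes "GI bleeding requiring hospitalization", qualifies perforation in the same way, limits delay to "Any procedure-related complication resulting in delay of surgery", and adds the general criterion "In-patient hospitalization or prolongation of existing hospitalization". Section 10.2.4 equates serious with grade 3 or higher.
- **What is collected.** Section 8.1.5 states that "AEs grade 1-2 will not be collected during the study", and 10.5 repeats this. Section 7.4.4 says: "Most gastrointestinal bleeding following endoscopy is self-limited and otherwise asymptomatic and not considered a serious complication".
- **Analysis.** Section 11.4.2.1 invokes the safety set, which 11.3.1 defines as everyone injected, but then says the incidence "will be determined for participants undergoing distal pancreas resections". It cites no event list and names no confidence interval method.

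**The concern.** Safety of the injection is a named secondary objective and half of the central hypothesis in Section 1.2. Few events are expected, so the estimate depends on which events count and for how long. Two analysts could follow the text faithfully and report different numerators from the same records.

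The more serious consequence concerns meaning. If the window extends past the resection, most of 2.2's list counts events whatever their cause. The reported figure would then mix harm from the injection with harm from a major pancreatic operation. Sections 11.3.1 and 11.3.2 keep those two apart, and 7.4.4 treats pancreatitis, bleeding and perforation as complications of the study intervention. In an open-label single-arm trial, settling the window and the list after the data are seen would weaken the estimate.

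**Working it through.** **Inputs.** Surgery is planned 7-14 days after injection (3.1). Up to 55 participants are injected to obtain 50 evaluable (Synopsis, 11.2). Endoscopy event counts come from Table 3. The plan states no expected rate, threshold or precision for this endpoint. The 55 reproduces as 50 × 1.10 = 55 (50/0.90 = 55.6 is nearly the same).

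**Step 1: end date.** Days from injection under each alternative in 2.2:

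| Surgery on day | Ends at surgery | 30 days after injection | 30 days after surgery |
|---|---|---|---|
| 7 | 7 | 30 | 37 |
| 14 | 14 | 30 | 44 |
| 42 (6-week limit in 8.5 and 11.3.2) | 42 | 30 | 72 |

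In the planned interval, the longest window is 44/14 = 3.1 to 37/7 = 5.3 times the until-surgery window. The postoperative share of the longest window is 30/44 = 68% to 30/37 = 81%, and 30/72 = 42% if surgery is at 6 weeks. The second and third alternatives in the table together reproduce 8.5: 30 days after surgery if operated, 30 days after injection if not. Stopping at surgery cannot be reconciled with that.

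**Step 2: attribution.** In 2.2, only the grade 3+ limb requires attribution to BTX. After the resection, hospitalized pancreatitis, hemorrhage and perforation therefore count whatever caused them. If the window ended at surgery, this would not arise.

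**Step 3: size per event.** The documents give no rate for these events after distal pancreatectomy, so only the effect of a single event can be shown (Clopper-Pearson 95% intervals):

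- 0/55 = 0% (0-6.5%)
- 1/55 = 1.8% (0.05-9.7%)

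For scale, Table 3 gives bleed 51 + pancreatitis 17 + perforation 5 = 73. Then 73/73,029 = 0.10%, and 0.0010 × 55 = 0.055 expected events. That is general endoscopy, so probably a low benchmark.

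**Step 4: event definition side by side.**

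| Item | 2.2 | 10.2.2 | 10.2.4 |
|---|---|---|---|
| GI bleeding, perforation | any | only if hospitalized | grade 3+ |
| Delay of surgery | any event | procedure-related only | no separate item |
| Attribution to BTX | grade 3+ limb only | none for the general criteria | none |

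Two consequences follow. As worded, 2.2 reaches grade 1-2 bleeding, which 8.1.5 and 10.5 say is not collected. A low-grade procedure-related complication that delays surgery is serious under 10.2.2 but falls below the 10.2.4 threshold. Bleeds are 51/73 = 70% of the three Table 3 categories. Table 3 gives no severity, so the number falling between the thresholds is unknown.

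**Step 5: delay data.** Section 8.5 records the reason when surgery does not take place, or when a delay is due to a BTX adverse event. Delay from any event, as 2.2 words it, is not fully covered.

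**The case against.** The strongest reply is that this is untidy wording in a descriptive endpoint, and that the text mostly resolves itself.

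- *Section 2.2 governs.* It says how the endpoint is defined, 10.2.2 is a general safety definition, and the Synopsis list is only an example. A reader might infer three rival definitions, but the example list does not support that. The conflict that stands is between 2.2, 10.2.2 and 10.2.4, with no cross-reference in 11.4.2.1 to settle it.
- *The surgery clause has a source.* Section 3.1 defines a post-treatment period that closes on the day of surgery, so the clause may be deliberate. That may explain it, but 2.2 does not ask for reporting by period, and one endpoint cannot have both ends.
- *The longer window is less widely stated than it looks.* Sections 3.1 and 11.4.5 use it only for the DSMC review of the first three participants. That is right. The trial-wide statements are in 8.5 and 10.5, and those two are enough.
- *Attribution is handled elsewhere.* Section 11.4.4 summarizes treatment-related SAEs. This helps, but it is a separate tabulation and leaves the named endpoint unchanged.
- *Uncollected bleeds cannot divide analysts.* Analysts sharing one dataset cannot differ on events that were never recorded. This stands; the defect is an endpoint wider than the data that support it.

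A reader might also infer that fistulas would be counted as injection SAEs. At the design rates of 2% and 11.2%, that would be 50 × 0.02 = 1.0 to 50 × 0.112 = 5.6 per 50 resected. It requires replacing 2.2 with 10.2.2, using the longer window, and assuming every fistula causes or prolongs a stay. Under 2.2, a fistula is not a listed event unless attributed to BTX.

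**Conclusion.** The point holds in two respects, with one clean-up. The end date in 2.2 contains an alternative that contradicts 8.5 and 10.5. Under the longer window, events caused by surgery enter a rate meant to describe the injection, with 68-81% of observation time postoperative when surgery is on schedule. The event definition in 2.2 conflicts with 10.2.2 and 10.2.4 on bleeding, perforation and delay, and extends to events the trial does not collect.

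A reader might infer from 11.4.2.1 that participants who never reach surgery leave the denominator. Read that way, two injected participants who lost surgery to a complication would turn 2/55 = 3.6% (0.4-12.5%) into 0/53 (0-6.7%). The documents do not support it: the same sentence names the safety set, 11.3.1 makes that set all injected, and 8.5 keeps unresected participants evaluable for safety. The phrase should go, but the intended denominator is hardly in doubt.

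The consequence is limited. The endpoint is descriptive, the run-in halt in 11.4.5 has its own criteria, and the primary analysis is unaffected. The size is one event's worth in 55. The total cannot be estimated because the documents give no postoperative rate for these events.

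**What to change.** 1. In 2.2, state one end-date rule that agrees with 8.5 and 10.5, and remove the alternative that stops at surgery.
2. In 11.4.2.1, delete the phrase about participants undergoing resection, so that the denominator is all injected participants, and specify an exact 95% interval as 11.4.1 and 11.4.2.2 do.
3. Report the rate separately for the two periods in 3.1: injection to surgery (or to 30 days after injection if there is no surgery), and surgery to postoperative day 30. Show postoperative events both regardless of cause and restricted to those graded definitely or possibly related under 10.2.5.
4. Reconcile 2.2, 10.2.2 and 10.2.4, with the Synopsis list, into one event definition limited to events the trial collects. It should settle the threshold for bleeding and perforation and the attribution of delay. Cite it in 11.4.2.1.
5. Record the reason for any surgical delay.

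The cost is wording in five places, one extra table and one added data item for delays. Onset and relationship are already collected under 10.5. The drawback is that the related-only count rests on unblinded clinician judgement, which is why the all-cause count should stand beside it.
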